7 MEASUREMENTS OF TREATMENT COMPLIANCE

7.1 Drug accountability

Listing of drug accountability for oral solution during the BRV Extension Period will be provided for the SS.

7.2 Treatment compliance

Treatment compliance will be analyzed for iv BRV administered during the study Evaluation Period. Treatment compliance will be calculated per subject per infusion for iv BRV. Noncompliance will be recorded for subjects who are administered <80% or >120% of the planned BRV dose.

Compliance will be calculated as 100 times the actual dose given during the infusion at particular time point based on the Study Drug Administration CRF and dividing this quantity by the planned infusion dose at that time point. For the Exploratory Cohort, planned iv BRV dose will be calculated as 0.5 mg times body weight (kg) per subject per infusion per time point. The last weight measurement prior to the first BRV dose will be taken for this calculation.

For the Confirmatory Cohorts, planned iv BRV dose (mg/kg) will be determined based on the evaluation of BRV plasma concentrations from the Exploratory Cohort.

Treatment compliance will also be analyzed for BRV Extension Period, the planned dose for oral BRV is the same dosage administered at the end of the Evaluation Period (i.e., BRV 0.5mg/kg bid for the Exploratory Cohort). The BRV dose should not be increased but can be decreased at the discretion of the Investigator. Therefore, noncompliance will be recorded only for subjects who are administered >120% of the planned oral BRV dose. For the Confirmatory Cohorts, the planned dose will be also the same dosage administered at the end of the Evaluation Period.

Listing of the calculated treatment compliance will be provided for the SS.

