^b The duration of the Baseline EEG depends on seizure activity. Subjects with intermittent seizures will enter the Evaluation Period based on at least 1 hour of EEG recording. Subjects in status epilepticus will enter the Evaluation Period based on up to 30 minutes of EEG recording, ie, as soon as 15 minutes of continuous seizures or 50% of cumulative seizure activity is confirmed on EEG.

^c If subjects do not benefit from BRV treatment after 96 hours of BRV administration, BRV administration will be stopped and replaced by another AED; however, the subject's participation in the study will continue. Subjects discontinuing BRV treatment during the Evaluation Period should start the Down-Titration Period while completing the Evaluation Period in parallel for the full 96 hours.

^d Parent(s) or legal representative(s) will be informed about the study as early as possible and asked to sign the informed consent after the occurrence of seizures is confirmed on VEEG. Continuous consent will be ensured by meetings between the Investigator (or designee) and the subject's parent(s) or legal representative(s), during the conduct of the study.

Table 5–2: Schedule of study assessments – Screening and Evaluation Periods (Confirmatory Cohorts)

Assessments	Screening Period ^a		Evaluation Period																			
	Up to 36h		Base-line Period ^b	0h	3h	6h	8h	9h	10h	12h	15h	18h	21h	24h	27h	34h	36h	48h	60h	72h	84h	96h ^c
	-36h to up to -1h	up to -1h to 0h																				
(Assessment window)	-	-	-	(±15min)											(±30min)							

^c The occurrence of ENS during the Baseline Period must be confirmed either by the local or central VEEG reader prior to drug administration. Preferably, the central VEEG reader should confirm the required ENS.

^f Measurement of body weight is optional at 24, 48, 72, and 96 hours. Dosage of BRV during the Evaluation Period will be based on the subject's weight measured prior to the start of the first BRV administration. However, dosage calculation can be adjusted to a more recent weight measurement, upon discretion of the Investigator, if weight is measured during the Evaluation Period.

^g Head circumference Baseline measurement should be taken within 7 days prior to drug administration, or at birth for subjects ≤7 days old.

^h Subjects will receive iv BRV 1mg/kg bid (2mg/kg/day), as recommended by the DMC on 05 Nov 2020 based on the results of the PK analysis of the Exploratory Cohort as well as an existing PK model from N01263.

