7.7 Procedures for monitoring subject compliance

After each iv BRV administration, empty/used BRV containers must be kept.

All unused IMP and empty IMP containers/bottles must be accounted for or returned to the site. For subjects treated at home during the BRV Extension Period, parent(s) or legal representative(s) should be advised to return all unused IMP and empty IMP bottles to the site. Drug accountability must be done in the presence of the subject's parent(s) or legal representative(s) and site staff to obtain explanations regarding discrepancies in compliance with the dosing regimen. Drug accountability must be recorded on the Drug Accountability form.

Site personnel who are administering iv BRV will record information about all doses administered, including the target dose, actual dose administered, and the dates and times of initiation and completion of each iv administration. If the actual dose is less or more than the target dose, the reason a partial or excessive dose was administered will be recorded.

Intravenous BRV solution will be administered under supervision of the Investigator or his/her designee. The noninjected volume will be recorded in the eCRF. Compliance with the recommended duration of the iv administration will also be assessed by recording the start time and the stop time in the eCRF.

Noncompliance will be recorded for subjects who are administered <75% or >125% of the planned BRV dose. If, in the Investigator's opinion, there is persistent noncompliance with the subject's BRV administration, the Sponsor, in conjunction with the Investigator, will make a decision as to whether the subject should be withdrawn from the study.

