3.6.3 Pharmacokinetic Per Protocol Set

The Pharmacokinetic Per-Protocol Set (PK-PPS) will consist of all subjects who provide at least one measurable post-Baseline plasma sample (with recorded sampling time) on at least 1 post-Baseline visit with documented study medication intake times. This analysis set will be used for the Exploratory Cohort and the Confirmatory Cohort(s). Subjects with important protocol deviations will be excluded from the PK-PPS.

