5.2 Protocol deviations

The number and percentage of FAS subjects with no important protocol deviations and at least 1 important protocol deviation will be summarized overall, and by main category of protocol deviation (Inclusion criteria deviation, Exclusion criteria deviation, Withdrawal criteria deviation, Prohibited concomitant medication, use incorrect treatment or dose, Treatment non-compliance, Procedural non-compliance). Additionally, the number and percentage of subjects excluded from the PK-PPS due to important protocol deviations will be summarized overall and by main protocol deviation category for the FAS. Other specific categories of protocol deviations will be defined within the IPD specifications document.

Listing of subjects excluded from PK-PPS will be provided.

Listing of important protocol deviations will be provided for the SS.

All completed COVID-19 Impact eCRF pages and other IPDs will be discussed in IPD meetings, including whether the deviation may have been caused by COVID-19.

All data collected from the COVID-19 Impact eCRF page will be listed only.

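### The SAP's BRV noncompliance limits (<80% or >120%) differ from the protocol's (<75% or >125%) without being declared, and its planned dose does not track the weight on which the protocol lets sites dose

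*SAP*

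**What the plan says.** **Limits.** Protocol 7.7: "Noncompliance will be recorded for subjects who are administered <75% or >125% of the planned BRV dose". SAP 7.2, for intravenous doses in the Evaluation Period: "Noncompliance will be recorded for subjects who are administered <80% or >120% of the planned BRV dose". For oral dosing in the Extension Period the SAP keeps only the 120% upper limit, because the investigator may lower the dose. SAP Table 3.1 (Section 3.10), which lists changes to protocol-defined analyses, contains only the seizure-cause subgroups. SAP 13.2 records that the noncompliance definition in 7.2 was updated at SAP Amendment 2, without a reason.

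**Denominator.** SAP 7.2 scores each infusion as 100 times the actual dose over the dose planned for it. The Exploratory rule reads "planned iv BRV dose will be calculated as 0.5 mg times body weight (kg) per subject per infusion", and the weight is then fixed by a separate sentence: "The last weight measurement prior to the first BRV dose will be taken for this calculation". The Confirmatory rule begins "For the Confirmatory Cohorts, planned iv BRV dose (mg/kg) will be determined" and relies on the Exploratory concentrations; neither a mg/kg figure nor a weight is given. The protocol starts from the weight before the first dose, but the footnotes to Tables 5-1 and 5-2 add: "However, dosage calculation can be adjusted to a more recent weight measurement, upon discretion of the Investigator". Sections 8.1.2 and 8.2.2 repeat this. Protocol 7.7 also has sites record both the target and the actual dose of every intravenous administration.

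**Consequence.** The main deviation categories in SAP 5.2 include "Treatment non-compliance, Procedural non-compliance". SAP 3.6.3 states: "Subjects with important protocol deviations will be excluded from the PK-PPS". SAP 3.5 and Protocol 13.6 put the criteria for important deviations in a separate specification document.

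**The concern.** One term has two definitions, so the same infusion can be reported as compliant or noncompliant depending on which document is followed. In addition, a baby dosed on a newer weight, as the protocol allows, is scored in the Exploratory Cohort against a dose that the site was no longer aiming for. For the Confirmatory Cohorts, planned at 36 or more of at least 42 subjects, the programmer has no complete formula.

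What is at stake is the PK-PPS. SAP 9.1 bases the PK tables on it, and PK is the primary objective. The numbers are small: the Exploratory Cohort is planned at 6 subjects, so one exclusion would be 1/6 = 17%. Each cohort is required to include only 2 subjects on hypothermia, so one exclusion could halve that subgroup.

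**Working it through.** The plan gives no figure to reproduce. The check is arithmetic on the SAP 7.2 formula.

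**1. The two pairs of limits.** Take the minimum enrolment weight of 2.3 kg (Protocol 6.1). At the Exploratory 0.5 mg/kg, the planned dose is 2.3 × 0.5 = 1.15 mg.

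| Share of plan | Dose |
|---|---|
| 75% | 0.8625 mg |
| 80% | 0.92 mg |
| 120% | 1.38 mg |
| 125% | 1.4375 mg |

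Doses from 0.8625 to <0.92 mg, and from >1.38 to 1.4375 mg, are compliant under the protocol and noncompliant under the SAP. At 1 mg/kg, the Confirmatory dose stated in Protocol 5.1.2, every figure doubles: 1.725 to <1.84 mg and >2.76 to 2.875 mg.

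**2. Weight alone (Exploratory rule).** Let w0 be the weight before the first dose and w1 the newer weight. A fully delivered re-based dose scores 100 × w1/w0. The weight changes here are assumptions, since the documents give none.

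| Weight change | Score after loss / gain | SAP flag |
|---|---|---|
| 5% | 95 / 105 | no |
| 10% | 90 / 110 | no |
| 15% | 85 / 115 | no |
| 20% | 80 / 120 | no |
| 21% | 79 / 121 | yes |

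Weight alone triggers a flag only beyond a 20% change, and in this cohort that would have to occur within a 48-hour Evaluation Period.

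**3. Weight combined with incomplete or excess delivery.** If a percentage d of the re-based target is delivered, the score is d × w1/w0. The SAP flags when d < 80/(w1/w0) or d > 120/(w1/w0).

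| Weight change | Flag if d below | Flag if d above |
|---|---|---|
| −15% | 94.1% | 141.2% |
| −10% | 88.9% | 133.3% |
| −5% | 84.2% | 126.3% |
| +5% | 76.2% | 114.3% |
| +10% | 72.7% | 109.1% |
| +15% | 69.6% | 104.3% |

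The error runs both ways. After a 10% loss, delivery of 85% of the re-based target scores 0.85 × 90 = 76.5%: a flag in the SAP, none under the protocol's limits on either denominator. After a 10% gain, delivery of 74% of target scores 0.74 × 110 = 81.4%: no flag in the SAP, although it is below 75% of the dose aimed for.

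**4. Confirmatory Cohorts.** The sentence that fixes the weight follows the Exploratory formula. Nothing equivalent follows for the Confirmatory Cohorts, so steps 2 and 3 do not follow from the SAP text there. The defect in those cohorts is a missing rule, not a contradiction.

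**5. Version lag.** SAP 1 cites Protocol Amendment 6. The Amendment 7 log (Protocol 17.7) shows no change to Section 7.7, so lag does not appear to explain the different limits. It may explain the missing Confirmatory mg/kg figure, which entered the protocol at Amendment 7.

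**The case against.** A reader might infer that correctly dosed babies will be flagged and will drop out of the PK set. The documents support neither half. A baby given exactly the re-based dose is flagged only if weight moves by more than 20%; at smaller changes a flag also needs under- or over-delivery. Leaving the PK-PPS is not established either. SAP 5.2 names a category of deviation but does not say that a 7.2 flag is an important deviation, the criteria are in a document not supplied here, exclusions are confirmed in review before database lock, and the only output that SAP 7.2 promises is a listing. These points stand.

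The primary PK variable is the concentration after the first dose. For that infusion both documents use a weight taken before dosing, so re-basing cannot change its score. That also stands. A later flag could touch first-dose data only if the specification treats it as an important deviation, because the exclusion is by subject.

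The change of limits appears in the SAP amendment log, and since Protocol 13 specifies no compliance analysis, it is arguable whether Table 3.1 had to list it. The log entry gives neither the old and new limits nor a reason, so a reader of the two documents still meets an unexplained conflict.

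Finally, dividing by the site's recorded target would score a miscalculated target as 100%. That is a fair criticism, so the recorded target needs a check against mg/kg and weight.

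**Conclusion.** The limits conflict by five percentage points on each side, and SAP 3.10 does not declare it. The Exploratory denominator mis-scores doses that the protocol permits to follow a newer weight, and the Confirmatory denominator is undefined. The realistic disagreements are infusions in the 75% to <80% and >120% to 125% bands, and re-based doses that were also not delivered in full or were exceeded. The rule may affect membership of the PK-PPS, depending on a deviation specification that is not available here. Efficacy is not affected, because SAP 3.6.2 does not exclude subjects with important deviations from the FAS. The conflict in limits rests on the text alone; the examples with re-based weights rest on assumed weight changes of 5% to 15%. The point should be resolved before the compliance listing is programmed and before deviations are classified.

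**What to change.** 1. Reconcile Protocol 7.7 and SAP 7.2 to one pair of limits, or declare the change and its reason in SAP 3.10. Say which limits apply to oral dosing.
2. In SAP 7.2, define the planned dose in every cohort on the weight actually used for that infusion: the recorded target dose, checked against the protocol mg/kg in force times that weight. The check keeps errors in the target visible.
3. State how per-infusion scores become a subject-level flag, and whether a 7.2 flag is an important deviation that excludes the subject from the PK-PPS. Align the deviation specification.

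The cost is mainly SAP wording and one derivation. Protocol 7.7 already requires the target dose to be recorded, but it names the eCRF only for the noninjected volume and the start and stop times, so confirm that the target dose and its weight reach the database. A protocol change is needed only if the protocol's limits are the ones to move.

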10.1 Extent of exposure

The duration of BRV exposure, is defined as the start date and time of last administration of study medication (BRV) minus the start date and time of first administration of study medication (BRV) plus duration of dosing interval (12 hours, however the dosing interval may be adjusted if results point into that).

The duration of iv BRV exposure during the Evaluation Period will be displayed in hours. The duration of exposure of iv BRV and oral BRV solution during the BRV Extension Period will be displayed in days.

The date and time of last administration of study medication is the maximum date and time from the CRFs “Study Medication Administration (Infusion)” and “Study Medication Administration (Oral Solution)”.

Exposure as categorical parameter will be summarized as number of doses received (1 dose, > 1 dose) and continuous parameter (in hours or days). For the continuous parameter, descriptive statistics for the duration of exposure to study medication in hours or days will be presented. For the number of doses, the number and percentage of subjects who received 1 dose and >1 doses will be summarized. Handling of study medication missing data is described in [Section 4.2.4](#).

Exposure as a continuous parameter will be categorized (>0-12 hours, >12-24 hours, >24-48 hours, >48-72 hours, >72-96 hours, >96 hours – 14 days, >14 days) by study periods for

Exploratory, individual Confirmatory Cohorts and for overall combined Confirmatory Cohorts for the SS.

The following listings will be provided:

- study medication administration,
- exposure to study medication BRV infusion, and
- exposure to study medication BRV oral solution.

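### SAP 7.2 records oral BRV noncompliance only above 120% of a fixed planned dose, so missed Extension-Period doses are never flagged, unlike under the two-sided rule in Protocol 7.7

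*SAP*

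**What the plan says.** Protocol 7.7 gives one rule: "Noncompliance will be recorded for subjects who are administered <75% or >125% of the planned BRV dose". It names neither a route nor a study period, and the same section deals with home dosing: "For subjects treated at home during the BRV Extension Period, parent(s) or legal representative(s) should be advised to return all unused IMP".

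SAP 7.2 gives two rules. For iv BRV in the Evaluation Period: "Noncompliance will be recorded for subjects who are administered <80% or >120% of the planned BRV dose". For oral BRV in the Extension Period: "noncompliance will be recorded only for subjects who are administered >120% of the planned oral BRV dose". The reason given is that "The BRV dose should not be increased but can be decreased at the discretion of the Investigator". The oral denominator is also set there: "the planned dose for oral BRV is the same dosage administered at the end of the Evaluation Period". A compliance formula is written out for infusions but not for oral dosing. The output is a listing: "Listing of the calculated treatment compliance will be provided for the SS".

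SAP 10.1 defines exposure duration separately. It "is defined as the start date and time of last administration of study medication (BRV) minus the start date and time of first administration", plus one 12-hour dosing interval. The last administration is the later of the latest infusion and the latest oral dose on the two administration CRFs.

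SAP Table 3.1 (section 3.10), which lists changes to protocol-defined analyses, contains only the cause-of-seizure subgroups. The SAP 13.2 change log notes that the noncompliance definition was updated, without a reason or any mention of the protocol rule.

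**The concern.** The Extension Period is the one part of the study in which parents may give the drug at home, so it is where missed doses are most likely. It is also where the SAP removes the lower compliance limit. The stated reason, that the Investigator may lower the dose, covers ordered decreases. It does not cover doses that were prescribed and not given, yet the rule treats the two alike.

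At stake is who is recorded as noncompliant, and how Extension-Period exposure is read. Adverse events are tabulated separately for that period. A reader of those tables needs to know how much of the prescribed drug the infants received.

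**Working it through.** Let c = 100 × dose administered / planned dose.

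**1. The three rules side by side**

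| c | Protocol 7.7 (<75 or >125) | SAP iv (<80 or >120) | SAP oral (>120) |
|---|---|---|---|
| 0% | recorded | recorded | not recorded |
| 50% | recorded | recorded | not recorded |
| 74% | recorded | recorded | not recorded |
| 77% | not recorded | recorded | not recorded |
| 100% | not recorded | not recorded | not recorded |
| 122% | not recorded | recorded | recorded |
| 126% | recorded | recorded | recorded |

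The SAP oral rule never fires for c between 0% and 120%. The rows at 77% and 122% show that the SAP iv limits also depart from the protocol. At 122% the SAP oral rule records a case that the protocol rule does not.

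**2. Missed doses.** The documents do not fix when oral dosing starts, so a start at day 7 of postnatal age is assumed. The end is day 35 (28 + 7 days, SAP 2.3.2). Twice-daily dosing gives 28 × 2 = 56 planned doses.

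- 14 missed: 42/56 = 75.0%, not below the protocol limit.
- 15 missed: 41/56 = 73.2%, recorded under the protocol.
- Under the SAP oral rule, no number missed, up to all 56, is recorded.

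Range over the assumed length:
- 7 days (14 doses): the protocol records from 4 missed (10/14 = 71.4%; with 3 missed, 11/14 = 78.6%).
- Day 7 to day 90 (83 × 2 = 166 doses), the prolonged extension allowed only when no long-term study is available: the protocol records from 42 missed (124/166 = 74.7%; with 41 missed, 125/166 = 75.3%).
- The SAP count is zero throughout.

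**3. The fixed denominator.** Suppose the Investigator halves the dose and the planned dose is not updated.

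- Every prescribed dose given: c = 50%, the same value as missing half of an unreduced dose.
- Twice the prescribed dose given: c = 2 × 50% = 100%, not recorded.
- Recording starts only above 120% / 50% = 2.4 times the prescribed dose.

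With the prescribed dose as denominator, full adherence to the halved dose gives 100% and is not recorded. Half of it given is 50% and twice it is 200%; both are recorded under 75/125 or 80/120. A lower limit can therefore be kept without penalising a permitted decrease.

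**4. Exposure duration.** Because duration is last start minus first start plus 12 hours, gaps between given doses count as exposed time. If every oral dose is missed, the last administration is the last infusion and exposure stops there. Exposure therefore misses gaps, but not total omission.

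**The case against.** The one-sided rule is deliberate. Decreases are allowed in the Extension Period, and against a fixed planned dose a lower limit would flag infants treated as the Investigator ordered. The protocol threshold also follows the paragraphs on iv administration, so an iv-only reading is possible. It sits outside the protocol's statistics section, so the sponsor may see no duty to enter it in Table 3.1. The first argument is a problem with the denominator and disappears once the prescribed dose is used. The second is a matter of placement: the text has no route limit, and the section covers home treatment. On the third, the change log shows the definition was edited but does not tell a reader that it departs from the protocol.

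Several other objections stand:
- Calculated compliance, oral drug accountability, study medication administration and oral exposure are all listed for the Safety Set. In a study of about 42 infants, a value of 0% or 50% can be seen on the page.
- Protocol 7.7 requires dosing discrepancies to be explained with the parents present, and sends persistent noncompliance to a joint Sponsor and Investigator decision on withdrawal. Neither depends on the SAP flag.
- Treatment noncompliance is also an important-deviation category (SAP 5.2), with criteria in a separate document not available here.

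A reader might infer that an infant who misses every home dose is classed as compliant and escapes notice in both compliance and exposure. The documents do not support this. The SAP applies no such label, the 0% would be listed, and exposure would end at the last infusion.

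A reader might also infer that adverse-event incidence is diluted. SAP 10.2.1 plans numbers and percentages of subjects by period, not exposure-adjusted rates, so neither the flag nor an inflated duration enters any of those figures.

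**Conclusion.** The point holds as a minor but real error in a stated rule. SAP 7.2 never records oral under-dosing as noncompliance, contrary to the wording of Protocol 7.7, and its fixed denominator also weakens the upper limit that it keeps. The differences in both the oral and the iv limits are undeclared in SAP 3.10.

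On the assumed 56-dose course, the protocol rule records noncompliance from 15 missed doses and the SAP rule from none. That count depends on the assumed start day and length; the SAP's zero does not.

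The effect is confined to the recording of noncompliance and the reading of Extension-Period exposure. Efficacy is assessed in the 96-hour iv Evaluation Period and at the end of Down-Titration, and scheduled BRV PK samples fall in the Evaluation Period, so neither is touched. The conclusion takes the protocol rule to cover oral dosing, as its wording does. If the sponsor means it for iv only, Protocol 7.7 should say so; the denominator problem would remain.

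**What to change.** In SAP 7.2:
- Define the planned oral dose as the dose currently prescribed by the Investigator, so that an ordered decrease resets the denominator.
- Give an oral compliance formula based on the oral administration CRF and the dosing diary. Use drug returns as support only: 300 mL bottles at 10 mg/mL are a coarse measure. At 1 mg/kg, 15 missed doses amount to 15 × 0.3 mL = 4.5 mL, or 1.5% of a bottle, for an assumed 3 kg infant. At the 2.3 kg entry minimum they amount to 15 × 0.23 = 3.45 mL, about 1.2%.
- Apply both a lower and an upper limit, reconciled with Protocol 7.7 for oral and iv dosing alike.

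Declare any remaining difference in SAP 3.10. In the SAP 10.1 outputs, report the number of planned oral doses not given beside exposure duration.

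The cost is SAP wording and some programming to follow changes in the prescribed dose. The protocol asks for target and actual dose to be recorded only for iv administration, so the sponsor must first confirm that the CRF captures ordered oral decreases.
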